7.3.2 Secondary Analyses

Analyses for secondary objectives will be mostly descriptive. Line listings as well as summary descriptive statistics including means, medians, and proportions with 95% exact or asymptotic confidence intervals as appropriate at each visit, will be used for the following secondary objectives. Specifically,

- Use GEE or random effects models to describe longitudinal patterns and their correlates of PrEP initiation and adherence among participants (e.g.: C4, substance use, sociodemographics, sociocultural factors, risk practices and incarceration)
- To describe side effects and toxicities of PrEP among participants in the PrEP demonstration project. AEs will be tabulated, overall and by grade. For any reasonably common AEs (> 20 events), exploratory analyses will be conducted to assess correlates of the AE, including demographics and duration and patterns of PrEP use, within the limits imposed by the small expected number of events.
- Describe and produce summary plots for longitudinal changes in sexual risk-taking behavior among study participants
- List and summarize reasons BMSM choose to initiate or decline PrEP
- List and summarize HIV seroconversions and characteristics of the infection(s) (e.g., viral set point, drug resistance patterns) in participants who initiated PrEP
- Use Kappa-statistics to assess agreement of adherence under different measures.

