2.2 Secondary Objectives

- To describe side effects, toxicities, risk compensation, and STIs among participants who initiate PrEP
- To describe patterns and attributes of PrEP initiation and adherence among participants (e.g., C4, substance use, sociocultural factors and incarceration)
- To measure changes in sexual risk taking behavior among study participants
- To describe reasons BMSM choose to initiate or decline PrEP
- To describe the number of HIV seroconversions, and to analyze viral characteristics (e.g., drug resistance) and the host response to infection in participants who become HIV-infected while on PrEP
- To characterize the participant perception of care and referral plans

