4.2 Study Product Regimen, Administration, and Duration

Once enrolled, all participants who agree to initiate FTC/TDF study product will be directed to take one FTC/TDF 200mg/300mg (Truvada[®]) tablet orally once daily with or without food for up to 52 weeks.

The participant can decide to initiate FTC/TDF administration at any time after enrollment and week 48 of the study treatment period. Once initiated, the study participant may also decide to discontinue taking FTC/TDF study product at any time during the 52 week study treatment period. For

participants who decide to initiate PrEP at or after Week 48, partnerships will be established as applicable with community partners in order to provide adequate clinical care and follow-up.

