- HIV/STI behavioral counseling (pre- and post-test), including risk-reduction counseling
- PrEP discussion
- Offer condoms and other prevention supplies
- Informed Consent for individual interview (Week 52 only)

Note: Indication and Usage for Pre-exposure Prophylaxis will be reviewed with participants as part of a comprehensive package of risk reduction services. In general, sites must refer to the CDC interim guidelines for PrEP administration

(http://www.cdc.gov/hiv/prep/pdf/PrEPfactsheet.pdf) and to the guidelines for PrEP Indication (https://www.truvadapreprems.com/#). A manual will be created for all sites to follow when introducing PrEP to participants based on safety and efficacy language found in the ICF under "Study Purpose".

If initiating or on PrEP:

- Assess participant's initial readiness for PrEP adherence (only if initiating; initiation not allowed to start after Week 48)
- Self-reported study product adherence assessment
- Study product supply (except Week 52)
- Autonomy supportive adherence counseling (except Week 52)

- PrEP Adherence Self-Regulation Questionnaire (participant self-administered) (except week 52)
- C4 including:
 - C4 Case Conference (commencing discharge/transition planning for weeks 39 and 52)
 - Care Coordination Measurement Tool (recorded by providers)
 - Health Care Climate Questionnaire (participant self-administered)
 - Client Perception of Coordination Questionnaire (participant self-administered)
 - Care Transition Measure (Week 52 only or study exit)
 - Front Line Administrative Staff Satisfaction Survey (week 52 only or study exit)

Clinical Evaluations/Procedures

- Interim medical history including concomitant medications
- Symptom-driven physical exam
- Hepatitis vaccination or referral, if indicated
- Blood collection
- Urine collection
- Rectal swab collection (Weeks 26 and 52 only)
- N MED ASSIST (Week 52 only)
- Submit discharge summary to primary health provider, when applicable
- STI treatment, if indicated (based on testing of samples collected at Weeks 26 and 52)

Laboratory Evaluations/ Procedures

- HIV testing per algorithm in the SSP Manual
- Renal function tests (BUN, creatinine for those on PrEP within the past 60 days)*
- Calculated creatinine clearance (for those on PrEP within the past 60 days)*
- Urine dipstick for protein and glucose
- STI testing: syphilis (Weeks 26 and 52 only)
- STI testing: rectal and urine NAAT for GC and CT (Weeks 26 and 52 only)

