6.3 Adverse Event (AE) Reporting

Adverse events (AE) are defined as any untoward medical occurrence experienced by participants during the study, and may or may not have a causal relationship with the treatment. Information regarding all AEs regardless of seriousness or severity will be recorded in the participant's source files. Grade 3 and higher adverse events and all creatinine AEs will be recorded on study CRFs. All STIs will be recorded in CRFs. All SAEs must be reported on AE Log CRF. All AEs that result in a clinical hold or permanent discontinuation of study product are reported on AE Log CRF regardless of grade. Grade 3 and higher clinical AEs will be referred to a study clinician at the time of the visit. All critical laboratory values will be reported as applicable per site SOPs. Participants who are not

present at the study site at the time a laboratory AE requiring retesting or follow-up is identified will be followed as deemed clinically appropriate. With appropriate permission of the participant, and whenever possible, records from non-study medical providers related to untoward medical occurrences will be requested and required data elements will be recorded on study CRFs and/or in the participant's medical chart. All AEs regardless of severity will be followed clinically, until the AE resolves or stabilizes as per the appropriate toxicity algorithm. AEs will be assessed from the time of enrollment in this PrEP demonstration project.

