6.5.1 Reporting to DAIDS

The DAIDS Adverse Event Reporting System (DAERS), an internet-based reporting system, must be used for EAE reporting to DAIDS. In the event of system outages or technical difficulties, EAEs may

be submitted via the DAIDS EAE form. For questions about DAERS, please contact DAIDS-ES at [contact]. Site queries may also be sent with the DAERS application itself.

Where DAERS has not been implemented, sites will submit expedited AEs by documenting the information on the current DAIDS EAE Form. This form is available on the RSC website: http://rsc.tech-res.com/safetyandpharmacovigilance/.

For questions about EAE reporting, please contact the RSC at [contact].

6.5.2 **Reporting Requirements for this Study**

The Serious Adverse Event (SAE) Reporting Category, as defined in Version 2.0 (or latest version) of the DAIDS EAE manual, will be used for this study. The study agents for the purposes of SAE reporting are part of a fixed dose combination tablet: emtricitabine (FTC)/tenofovir disoproxil fumarate (TDF).

The SAE reporting period for this study is per the DAIDS EAE manual and continues from enrollment of a trial participant to the end of trial follow-up for that participant. All reportable SAEs occurring during the study reporting period will be reported to the principal investigator and the DAIDS Regulatory Support Center (RSC) Safety Office in an expedited manner, within three reporting days of site awareness of the events (see definition in Appendix D of the DAIDS EAE Manual).

After the protocol-defined AE reporting period, only SUSARs as defined in Version 2.0 of the DAIDS EAE manual will be reported to DAIDS if the study staff become aware of the events on a passive basis (from publicly available information).

Reporting requirements for the local IRBs will also be followed.

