7.2 Sample Size Consideration

A total sample size of 225 BMSM participants will be recruited into the study. Each participant will be enrolled to receive C4 and offered daily PrEP for at least 12 months.

According to the primary objective, two primary endpoints are considered: (1) PrEP initiation measured by the acceptance rate of the BMSM who are offered PrEP, and (2) PrEP adherence measured by the percentage of PrEP adherence among the BMSM who choose PrEP.

For the PrEP initiation endpoint, Table 3 lists the two-sided 95% confidence intervals for the true percentage of the PrEP acceptance rate for the BMSM who are offered PrEP. For example, if the observed PrEP acceptance rate is 50%, then there is 95% chance that the range of 44% - 57% will contain the true PrEP acceptance rate.

Table 2: 95% Confidence Intervals for the True PrEP Initiation Given by Possibly Observed PrEP Percentages

Ν	Observed PrEP Acceptance Rate	95% CI for True PrEP Acceptance Rate
	33%	(27%, 39%)
225	50%	(44%, 57%)
	67%	(61%, 73%)

For the PrEP adherence endpoint, Table 4 lists the two-sided 95% confidence intervals for the true percentage of the PrEP adherence rates for the BMSM who actually receive PrEP, assuming a 10% to 20% loss-to-follow-up (e.g. including those lost due to incarceration) during the 12-month period. For example, if the PrEP acceptance rate is 50% and an observed adherence rate is 67%, then there is 95% chance that the range 58%-76% will contain the true PrEP adherence rate.

Table 3:95% Confidence Intervals for the True PrEP Adherence Rate Given by Possibly
Observed PrEP Adherence Percentages

PrEP Acceptance Rate	PrEP Adherence Rate	95% CI for True PrEP Adherence Rate
----------------------	---------------------	--

		10% LTFP*	20%LTFP*
	33%	(22%, 44%)	(21%, 45%)
33% (low)	50%	(38%, 62%)	(37%, 63%)
	67%	(56%, 78%)	(55%,79%)
	33%	(24%, 42%)	(23%, 43%)
50% (moderate)	50%	(40%, 60%)	(39%, 60%)
	67%	(58%, 76%)	(57%,77%)
67% (optimistic)	33%	(25%, 41%)	(25%,41%)
	50%	(42%, 58%)	(41%,59%)
	67%	(59%, 75%)	(59%.75%)

*LTFP: Loss-to-Follow-up

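### The AE table in Protocol section 7.3.2 is worded for all participants, although the safety objective is limited to men who initiate PrEP

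*Protocol*

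**What the plan says.** The secondary safety objective (Protocol, section 2.2, same words in the schema) is: "To describe side effects, toxicities, risk compensation, and STIs among participants who initiate PrEP". The analysis offered for it in section 7.3.2 is: "To describe side effects and toxicities of PrEP among participants in the PrEP demonstration project. AEs will be tabulated, overall and by grade". That bullet sets no split by initiation and no starting point at first dose. The seroconversion bullet in the same section, by contrast, is expressly limited to men who initiated PrEP.

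Three other parts of the protocol bear on how the bullet would be carried out:

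- **AE collection (section 6.3):** "AEs will be assessed from the time of enrollment in this PrEP demonstration project". For SAEs, section 6.5.2 says that the reporting period "continues from enrollment of a trial participant to the end of trial follow-up for that participant". Neither depends on PrEP use.
- **PrEP use (section 4.2):** "The participant can decide to initiate FTC/TDF administration at any time after enrollment and week 48 of the study treatment period", and once started, "the study participant may also decide to discontinue taking FTC/TDF study product at any time during the 52 week study treatment period". Men are enrolled and followed whether or not they ever take it.
- **Renal tests:** sections 5.4 and 5.5 list creatinine at Weeks 4 and 13 without restriction to users. From Week 26, section 5.6 restricts it: "Calculated creatinine clearance (for those on PrEP within the past 60 days", with the same limit on BUN and creatinine. Appendix IA footnote 12 words that restriction for Week 52 only.

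**The concern.** The objective and its analysis name different populations. In most trials this would be a slip of little consequence, because nearly everyone enrolled is treated. Here the share of men who accept the drug is itself a primary endpoint, and the protocol plans for it to be as low as one third.

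If the table follows 7.3.2 literally, events in men who never took a tablet, and events before a late starter's first dose, sit under a heading about toxicities of PrEP. Unexposed men also enlarge the denominator. The two effects pull in opposite directions: background events add to the count, while effects of the drug are diluted. Zero counts for rare events look more reassuring than they are. Section 1.2 gives as part of the rationale whether side-effect profiles differ from those of other MSM, and a table mixing users with non-users is a weak basis for that.

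**Working it through.** The protocol states no AE rate, safety-set size or safety precision, so there is no safety figure to reproduce.

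**Inputs.** Section 7.2: "A total sample size of 225 BMSM participants will be recruited into the study". Tables 2 and 3 of that section give acceptance scenarios of 33%, 50% and 67%. As a check that these refer to all 225 men, p ± 1.96·√(p(1−p)/225) gives 26.9–39.1%, 43.5–56.5% and 60.9–73.1%, which agrees with Table 2 to within a point. Using n = 225 × acceptance × (1 − loss) agrees with Table 3 to within a point. So the adherence planning already restricts itself to initiators, which the AE bullet does not.

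**Step 1: who would be in the table.**

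| Acceptance a | Initiators 225·a | Never-users 225·(1−a) |
|---|---|---|
| 33% | 74.25 | 150.75 |
| 50% | 112.5 | 112.5 |
| 67% | 150.75 | 74.25 |

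**Step 2: dilution.** Let q be the AE proportion in initiators and b that in never-users. An all-enrolled table shows a·q + (1−a)·b. If b = 0, this is a·q, that is 0.33 to 0.67 of q, an understatement by a factor of 1/0.67 = 1.5 to 1/0.33 = 3.0. The values of q and b below are assumptions for illustration.

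| Assumed q, b | a = 33% | a = 50% | a = 67% |
|---|---|---|---|
| 10%, 0% | 3.3% | 5.0% | 6.7% |
| 10%, 5% | 6.65% | 7.5% | 8.35% |
| 20%, 10% | 13.3% | 15.0% | 16.7% |

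**Step 3: no events seen.** The one-sided 95% upper limit is 1 − 0.05^(1/n). With n = 225 it is 1.3%. Among initiators only, it is 4.0% (n = 74), 2.6% (n = 112) or 2.0% (n = 151).

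**Step 4: creatinine.** Count the scheduled post-enrollment tests. A man on PrEP throughout has five (Weeks 4, 13, 26, 39, 52). A never-user has two under section 5.6 (Weeks 4 and 13), or four if footnote 12 is read as restricting Week 52 alone (Weeks 4, 13, 26, 39). Ascertainment in non-users is lower on either reading, but how much lower depends on which text is followed.

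**The case against.** The best case for the plan is that the objective governs and the phrase in 7.3.2 is only loose. Section 7.3.1 uses almost the same phrase for persistence, where it can only mean initiators, and toxicities of PrEP presuppose exposure. Section 7.3.2 prints no denominator and no time window, and the enrollment start in section 6.3 is a collection rule. Safety sets and on-treatment windows are commonly left to the SAP.

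This has weight, and a reader should not infer that the protocol fixes 225 as the AE denominator. But in 7.3.1 persistence is anchored by its definition, from PrEP start, and the AE bullet has no such anchor. The neighbouring seroconversion bullet shows that the population was limited when that was intended. At best two readings remain, differing up to 3.0-fold. The point is a mismatch within the protocol text, not a detail missing from it.

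The protocol also has partial safeguards. Relatedness to FTC/TDF is assessed for every AE (section 6.4.2), line listings are planned, exposure is explored as a correlate, and the monitoring committee may look at data by PrEP use (section 6.1). However, 7.3.2 does not tabulate by relatedness, and relatedness does not alter the denominator. The exposure analysis is exploratory and confined to AEs with more than 20 events, while the same bullet expects few. The committee split is optional. Because the number of initiators will be reported, a reader could undo the dilution for events known to occur only in users, but not where background events are mixed in.

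**Conclusion.** The mismatch stands: the analysis wording in 7.3.2 does not match the population of the objective it serves. Followed literally, it brings in about 74 to 151 never-users out of 225, plus time before initiation. A toxicity confined to users would show at about 0.33 to 0.67 of its true proportion. That size rests on the protocol's planning range for acceptance, on an all-enrolled denominator, and on no such events in non-users. The analysis is secondary and mostly descriptive, so this is a correction that should be made rather than a threat to the primary results.

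Four stronger inferences are not supported:

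- **Events after stopping are wrongly included.** The objective covers men who initiate, with no on-treatment limit, so those events fall within it.
- **Non-users cannot show a creatinine event.** They are scheduled for tests at Weeks 4 and 13, and the texts disagree on Weeks 26 and 39.
- **Comparison with other PrEP cohorts becomes impossible.** It is weakened, and section 7 plans no such comparison.
- **Exact time on and off PrEP is already available.** Discontinuation is defined in section 7.3.1 by ACASI self-report of 30 or more consecutive missed days. Appendix IA schedules ACASI only at enrollment and Weeks 13, 26, 39 and 52, so exact last-dose dates are not shown to exist.

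**What to change.** 1. In section 7.3.2, tabulate AEs by grade among participants who initiated PrEP, counting from first dose. Show events before initiation and in never-initiators in a separate column as background. The timing of initiation is already to be documented (section 7.1).
2. Treat a further split by time on and off PrEP as optional, and state that it is limited by the precision of the stop dates.
3. For creatinine events, use as denominator the men with a post-baseline creatinine result, and note the lower ascertainment in non-users after Week 13.
4. Reconcile section 5.6 with Appendix IA footnote 12 on who is tested at Weeks 26 and 39. Which schedule applies is for the protocol team to decide.

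The cost of items 1 to 3 is a paragraph of wording and one table column. Item 4 is a text correction. The main table needs no data beyond what the protocol already plans to collect.

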6.7.1 Discontinuation of Study Medication

Grades 1 or 2

Continue FTC/TDF at the discretion of the site investigator.

Grade 3

FTC/TDF may be continued at the discretion of the site investigator if a Grade 3 toxicity is considered to be unrelated to the study medication. Study medication will be temporarily withheld if Grade 3 toxicity is considered to be related to the study medication. After a Grade 3 toxicity returns to Grade 1, the participant can be reintroduced to medication after consultation with the site investigator, DAIDS Medical Officer, and other members of the PSRT. If a Grade 3 toxicity recurs and is considered to be related to study medication, FTC/TDF will be permanently discontinued.

Grade 4

For all Grade 4 laboratory-identified or clinical toxicities, FTC/TDF will be withheld unless it is determined to be not related. If a Grade 4 laboratory toxicity is not confirmed by repeat testing, it should be managed per algorithm for the new toxicity grade. Participants with Grade 4 AEs will be followed until the event resolves to baseline or stabilizes. Study drug may be restarted in the event of the resolution of a Grade 4 AE back to Grade 1, after consultation with the site investigator, DAIDS Medical Officer, and other members of the PSRT. If the toxicity recurs to Grade 3 or higher after FTC/TDF is restarted and is considered to be related to FTC/TDF, the study medication will be permanently discontinued.

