HIV testing will be performed with confirmation if necessary at all study visits per procedures outlined in the SSP. HIV RNA and genotyping will be performed at the NL on samples confirmed to be HIV infected.

Adverse events

Measurement of AEs will be graded via the DAIDS Toxicity Grading System determined by review of reported adverse events (clinical and laboratory) during the study.

Sexually transmitted infections (STIs)

STIs will be measured at baseline, monthly for the first three months and then at quarterly visits. Tests will include rectal and urine GC/CT, and NAAT for syphilis and chlamydia.

Participant perception of care and referral plans

Participant Perception of care and referral will be assessed via interviewer-administered questionnaire at Weeks 13, 26, 39 and 52.

Exploratory endpoints:

Dried Blood Spots Assessment

To assess PrEP adherence via DBS assessment of study drug and anabolite concentrations for TFV, FTC, FTC-TP and TFV-DP using semi-quantitative methods, and to compare it with adherence measured by drug concentrations in plasma and PBMC. Semi-quantitative methods will be used given the lack of known precision of the current DBS analytical methods and present/not present interpretations may be needed. Use of DBS testing for off-study ARV drug use may also be explored.

ARV Testing using a Multi-drug Screening Assay

Stored plasma samples will also be tested using a high-throughput multi-drug ARV screening assay. Results from this assay will be compared to other Pharmacologic assessments of adherence, and to assess off study ARV drug use.

Cost Characterization

Since the intervention may provide good value for the money spent (e.g., the cost of a vaccine vs. the cost of treating those who are infected), cost characterization will be described regarding space and staff needs for administering PrEP.

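### Section 7.3.2 tabulates adverse events overall and by grade, but under 6.3 an ordinary Grade 1-2 event must reach a case report form only if it led to a hold or discontinuation

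*Protocol*

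**What the plan says.** The first secondary objective (Protocol 2.2) is "To describe side effects, toxicities, risk compensation, and STIs among participants who initiate PrEP". To serve it, 7.3.2 states "AEs will be tabulated, overall and by grade", and adds exploratory correlate analyses, including duration and patterns of PrEP use, for any event type with more than 20 events. An introductory sentence in the same section allows for "proportions with 95% exact or asymptotic confidence intervals as appropriate at each visit".

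What is collected is set in 6.3. All events go into the site's own records: "Information regarding all AEs regardless of seriousness or severity will be recorded in the" source file of the man concerned. Entry on case report forms is narrower: "Grade 3 and higher adverse events and all creatinine AEs will be recorded on study CRFs". STIs and serious adverse events are also entered, and "All AEs that result in a clinical hold or permanent discontinuation of study product are reported on AE Log CRF regardless of grade".

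For Grades 1 and 2, 6.7.1 leaves study drug to local judgment: "Continue FTC/TDF at the discretion of the site investigator". Section 7.1 defines the adverse event endpoint as graded and "determined by review of reported adverse events (clinical and laboratory) during the study". Section 10.3 has study data sent to the statistical center for entry, cleaning and analysis, and names case report forms and other study instruments as the collection tools. It describes no transfer of adverse events held only in source files.

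**The concern.** The collection rule and the analysis rule do not fit together for one class of events: Grade 1-2 events that are not serious, not creatinine events and not STIs, called ordinary Grade 1-2 events here. For these, having to be entered depends on what was done with the drug and not on whether the event occurred. A table of all grades built on that collection gives an overall count and Grade 1-2 entries that look like frequencies but are partly counts of treatment interruptions.

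At stake is one part of the first secondary objective. Frequency would be too low, and mild side effects would look more treatment-limiting than they are. Events never entered cannot be restored at the analysis stage.

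**Working it through.** The protocol gives no figure for this point, so there is none to reproduce. The check sets the sections side by side; the arithmetic after that is illustration under assumed values.

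**1. What 6.3 brings onto a case report form**

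| Event | Entry required? |
|---|---|
| Grade 3 or higher | Always |
| Creatinine event, any grade | Always |
| STI | Always |
| Serious event, any grade | Always |
| Other Grade 1-2 event, drug held or stopped | Yes |
| Other Grade 1-2 event, drug continued | No; source file only |

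The first four rows are complete. The last two split ordinary Grade 1-2 events by drug action, and under 6.7.1 that action is a site decision.

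**2. Other routes into the database.** Under 6.3, data from outside providers may go on forms or only into the chart, so entry of mild events is not assured. Section 6.9 records medications used to treat adverse events, not the graded event itself. Neither completes the table.

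**3. Size.** Let T be the true number of ordinary Grade 1-2 events among initiators and h the share that lead to a hold or discontinuation. The recorded number is R = h × T, so the count is understated by a factor 1/h. The protocol gives neither T nor h. Over an assumed range:

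- h = 5%: 20-fold
- h = 10%: 10-fold
- h = 25%: 4-fold
- h = 50%: 2-fold
- h = 100%: complete

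Example, with assumed values except the 225 and the 50% acceptance scenario from 7.2: 225 × 0.50 gives about 112 initiators. If 30% (about 34 men) have one such event each and h = 10%, about 3 are recorded, and 3/112 = 2.7%.

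The factor 1/h applies to events, or to men with one event each. Counting men with repeat events, the loss is smaller: with three independent events and h = 25%, the chance that at least one is recorded is 1 - 0.75³ = 0.58, an understatement of 1/0.58 = 1.7-fold.

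**4. Correlate analyses (illustration only).** To reach 21 recorded events, an event type seen only at ordinary Grades 1-2 needs 21/h true events: 420 at h = 5%, 210 at 10%, 84 at 25%, 42 at 50%. Taking one event per man and a recorded count that is Binomial(N, p × h), with p the assumed true frequency, the chance of more than 20 recorded events at h = 50% is 0.0035, 0.16 and 0.67 for p = 20%, 30% and 40% with N = 112. With N = 151 (67% acceptance) it is 0.68 and 0.98 for p = 30% and 40%. For p up to 40% and h up to 25% it is at most 0.004 (N = 112) or 0.08 (N = 151).

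Where such an analysis runs, outcome and covariate are tied together. An ordinary Grade 1-2 event is recorded because drug was stopped, and stopping drug alters the duration and pattern of use under study. Such an event in a man not taking PrEP has no drug to hold, so no entry is required.

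**The case against.** The best defense reads 7.1 and 6.3 together. The endpoint is defined by reported events, 6.3 fixes what is reported, and so the 7.3.2 table covers reported events only. Selective collection is a legitimate choice for an approved drug, and row labels and caveats are often left to the analysis plan. The study is uncontrolled and its secondary analyses are mostly descriptive, so no between-arm comparison is biased. All events are still kept in source files and followed clinically.

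Much of this stands. Collection need not change, and participant safety is not in question. But the word reported in 7.1 does not tell a reader that ordinary Grade 1-2 entries are selected on drug action. An analysis plan could restrict or label the table but could not recover the missing events. The point is also not an absent detail: the two sections, followed as written, give a table that does not describe what 7.3.2 says it describes.

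Three stronger readings are tempting and are not supported:

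- A reader might infer that all Grade 1-2 rows hold only drug-stopping events. They do not: creatinine events, STIs and serious events are entered at any grade, and renal toxicity is the toxicity that 7.1 singles out for evaluation.
- A reader might infer that the protocol commits to confidence intervals for Grade 1-2 frequency that would miss the truth. The adverse event bullet promises a tabulation; intervals come from a general sentence and apply as appropriate.
- A reader might infer that the correlate analyses would rarely run. That depends on the assumed values, as the range from 0.0035 to 0.98 at h = 50% shows. The threshold also counts events of any grade, not men with one mild event.

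**Conclusion.** The point holds for ordinary Grade 1-2 events and for the overall count that includes them. Both would understate side-effect frequency and over-represent treatment-limiting events, and correlate analyses of these events against duration or pattern of PrEP use would be distorted in the same way. The direction follows from the text of 6.3 and 7.3.2, provided that some ordinary Grade 1-2 events do not lead to a hold and that sites enter what 6.3 requires. The size is unknown because it depends on h; every fold figure and probability above is illustration. Grade 3+, creatinine, STI and serious-event summaries and both primary endpoints are unaffected. Severity is minor: one descriptive secondary analysis is touched.

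**What to change.** In 7.3.2:

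- Limit the overall and by-grade tables and the correlate analyses to the categories that 6.3 captures fully: Grade 3 and higher, all creatinine events, STIs and serious events.
- List other Grade 1-2 events that led to a hold or discontinuation separately, as reasons for interruption.
- State that the frequency of ordinary Grade 1-2 side effects is not estimated.

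This is a change of text with no data cost. Its price is saying openly that part of the side-effect objective is not met at the lower grades.

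Only if the sponsor wants those side effects described, 6.3 could add a short prespecified list of expected FTC/TDF side effects, logged at each visit whether or not drug is held, with action on study drug as a separate field. That adds data entry and cleaning, and the sponsor may reasonably decline it.
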